## 12. APPENDIX A: OPTIONAL THIRD mRNA-1273 VACCINATION SUBSTUDY

All aspects of the main study apply to this substudy unless otherwise specified in [Section 12, Appendix A](#).

### 12.1 Overview

All subjects in this clinical trial were scheduled to receive two mRNA-1273 vaccinations, 28 days apart, at dosages of 25, 50, 100, or 250 mcg (see [Table 1](#)), with the last scheduled follow-up visit occurring at 365 days after the second vaccination (see [Table 4](#)). During the course of the main study, interim efficacy data from a Phase 3 placebo-controlled clinical trial of mRNA-1273 (COVE), administered as 2 doses of 100 mcg given 28 days apart, demonstrated vaccine efficacy of 94.1% (95% CI: 89.3%, 96.8%) for the prevention of symptomatic, confirmed COVID-19 (Baden, LR, et al. 2020). After review of the interim safety and efficacy data from that clinical trial, the FDA granted on December 18, 2020 an Emergency Use Authorization (EUA) for the mRNA-1273 vaccine in adults 18 years of age and older.

To potentially enhance and extend the duration of protection provided by the 2-dose vaccination schedule of mRNA-1273 administered in the main study, and to gain an understanding of the immune responses to a third dose of mRNA-1273, subjects in the main study may participate in an optional third mRNA-1273 vaccination substudy, detailed in [Section 12, Appendix A](#).

Substudy subjects will receive a third mRNA-1273 vaccination, administered via an IM injection at a dosage of 100 mcg/0.5 mL, given six to twelve months after receipt of their second vaccination in the main study. Substudy subjects will be followed for safety, reactogenicity, and immunogenicity endpoints through 12 months post third vaccination (Substudy Day 366).

To be eligible to participate in the substudy, subjects must have received both the first and second mRNA-1273 vaccinations in the main study. Other eligibility criteria are specified in [Appendix A](#). Subjects who received only one mRNA-1273 vaccination in the main study will be advised to receive an FDA authorized or approved COVID-19 vaccine, according to the recommended schedule, when available to them outside of this trial, unless they have a contraindication to COVID-19 vaccines that are available.

Subjects who elect not to participate in the optional third mRNA-1273 vaccination substudy or are not eligible for the substudy will continue to be followed according to the Schedule of Activities for the main study (see [Table 4](#)) with the Final Study Visit 14 occurring at Day 394 ( $\pm 14$  days).

Dosing for the optional third mRNA-1273 vaccination substudy is found in [Table 13](#).

Schedule of assessments for the optional third mRNA-1273 vaccination substudy is found in [Table 14](#).

Statistical Considerations for the optional third mRNA-1273 vaccination substudy are found in [Section 12.11](#).

### 12.2 Background and Scientific Rationale

See [Section 2.1](#) for additional background information.

In December 2019 the Wuhan Municipal Health Committee identified an outbreak of viral pneumonia that was ultimately identified as a novel pathogen named SARS-CoV-2. The disease caused by SARS-CoV-2 is called Coronavirus disease 2019 (COVID-19). On January 30, 2020, the International Health Regulations Emergency Committee of the World Health Organization (WHO) declared the COVID-19 outbreak a Public Health Emergency of International Concern. On January 31, 2020, the US Department of Health and Human Services declared a public health emergency in the United States. On March 11, 2020 the WHO declared COVID-19 a pandemic. As of January 10, 2021, the Center for Systems Science and Engineering (CSSE) at Johns Hopkins University ([systems.jhu.edu](http://systems.jhu.edu)) reports a global tally of 89,960,893 cases and 1,931,083 deaths and a total of 22,227,722 cases and 373,331 deaths in the United States. Morbidity and mortality have disproportionately affected older adults, and racial and ethnic minority populations (Garg S et al, 2020).

Despite success in developing a novel antiviral – remdesivir (Beigel JH et al, 2020), use of steroids and other novel immunomodulators (Kalil AC et al, 2020; Recovery Collaborative Group et al, 2020), and use of monoclonal antibodies (Chen P et al, 2020) for prevention and treatment of SARS-CoV-2 infection and COVID-19 disease, mortality remains substantial. Therefore, there is an urgent public health need for vaccines against SARS-CoV-2. Currently, there are over 170 vaccines in preclinical development and 60 vaccines that have entered into clinical trials (<https://www.who.int/publications/m/item/draft-landscape-of-covid-19-candidate-vaccines>). In the US, 2 mRNA vaccines [Moderna (mRNA-1273), Pfizer-BioNTech (BNT162b2)] received FDA EUA in December 2020.

confirmation clinical trial of mRNA-1273 (Jackson LA et al, 2020). Binding and neutralizing antibodies, and T cell responses were dose-dependent (Jackson LA et al, 2020; Anderson EJ et al, 2020). Responses at 1 month after the second dose were generally greater than those observed in sera of patients convalescing from COVID-19. A CD4 cytokine response occurred particularly among type 1 helper T cells.

Although declines in binding and neutralizing antibodies are observed by 3 months after the boost dose, recipients that had received 100 mcg of mRNA-1273 still had binding and neutralizing antibody titers that were similar to or exceeded that of convalescent sera (Jackson LA et al, 2020; Anderson EJ et al, 2020; Widge AT et al, 2020). Data through 6 months after the boost dose are pending.

A Phase 2 placebo-controlled, dose-confirmation clinical trial of mRNA-1273 (NCT04405076) is being conducted in adults using a prime-boost regimen of 50 mcg, 100 mcg, or placebo in 18- <55 year old and  $\geq$ 55 year old subjects. This trial is ongoing, but publicly available data are limited.

A Phase 3 placebo-controlled clinical trial of mRNA-1273 (NCT04470427, the COVE study) was initiated at almost 100 sites in the United States that enrolled 30,420 adults and administered two doses of either 100 mcg of mRNA-1273 or placebo (saline) (Baden LR et al, 2020). Risks to subjects receiving mRNA-1273 were primarily mild to moderate injection site reactions, particularly pain. Delayed injection-site reactions (those with onset on or after day 8) were noted in 244 subjects (0.8%) after the first dose and in 68 subjects (0.2%) after the second dose. Systemic reactions were transient and included fever, fatigue, chills, headache, myalgias, and arthralgias. Solicited systemic adverse events occurred more often in the mRNA-1273 group than in the placebo group after both the first dose (54.9%, vs. 42.2%) and the second dose (79.4%, vs. 36.5%). The severity of the solicited systemic events increased after the second dose in the mRNA-1273 group, with an increase in proportions of grade 2 events (from 16.5% after the first dose to 38.1% after the second dose) and grade 3 events (from 2.9% to 15.8%). Solicited systemic adverse events in the mRNA-1273 group lasted a mean of 2.6 days and 3.1 days after the first and second doses, respectively. Both solicited injection-site and systemic adverse events were more common among younger subjects (18 to <65 years of age) than among older subjects ( $\geq$ 65 years of age). Serious adverse events were rare, and the incidence was similar in the two groups. The frequency of grade 3 adverse events in the placebo group (1.3%) was similar to that in the vaccine group (1.5%), as were the frequencies of medically attended adverse events (9.7% vs. 9.0%) and serious adverse events (0.6% in both groups). Hypersensitivity reactions were reported in 1.5% and 1.1% of subjects in the vaccine and placebo groups, respectively.

In the primary efficacy analysis of the Phase 3 placebo-controlled clinical trial of mRNA-1273 (COVE), 196 cases of COVID-19 were diagnosed: 11 cases in the vaccine group (3.3 per 1000 person-years; 95% CI, 1.7 to 6.0) and 185 cases in the placebo group (56.5 per 1000 person-years; 95% CI, 48.7 to 65.3), indicating 94.1% efficacy of the mRNA-1273 vaccine (95% CI, 89.3 to 96.8%;  $P < 0.001$ ) for the prevention of symptomatic SARS-CoV-2 infection as compared with placebo. Findings were similar across key secondary analyses, including assessment starting 14 days after dose 1. Thirty subjects in the trial had severe COVID-19; all 30 were in the placebo group (indicating vaccine efficacy against severe COVID-19 of 100% [95% CI, could not be estimated to 1.0]), and one death among these subjects was attributed to COVID-19. The vaccine

efficacy to prevent COVID-19 was consistent across subgroups stratified by demographic and baseline characteristics.

It has been observed that antibodies may decline in patients previously infected with mild SARS-CoV-2 and that reinfection can occur (although perhaps infrequently symptomatic) (Ibarrondo FJ et al, 2020; Lumley SF et al, 2020). T cells and memory B cells are established after initial infection and remain present through 6 months after initial infection (Hartley GE et al, 2020). Additionally, the correlate or correlates of protection against COVID-19-related disease are not known, although active investigations are underway. Samples obtained from the Phase 3 clinical trials may provide insight into the correlate or correlates of protection.

The durability of the immune response to mRNA-1273 remains uncertain beyond 3 months after the second vaccination (Widge AT et al, 2020). Immune responses after vaccination in general are known to wane, sometimes to the point where wild-type disease can occur. Since immunity after natural SARS-CoV-2 infection is not lifelong and no correlate of protection has been identified yet, a study to assess the safety, reactogenicity, and immunogenicity of a third dose of mRNA-1273 is warranted. Additionally, some subjects in this trial have received less (25 and 50 mcg) than the 100 mcg dosage utilized in the Phase 3 placebo-controlled clinical trial of mRNA-1273 (COVE) that resulted in the EUA for mRNA-1273. These subjects could directly benefit from an additional vaccination that might boost their serological and cellular responses. Since T cells and memory B cells are established after initial infection through at least 6 months, it is likely that SARS-CoV-2 revaccination will result in robust serological responses, even among those that received less than the authorized dose (e.g., 25 mcg, 50 mcg) of mRNA-1273.

### **12.2.1 Justification for Dose**

It is not known whether a third mRNA-1273 vaccination will elicit immune responses or enhance immunity elicited by the 2-dose vaccination schedule of mRNA-1273 administered in the main study. If such responses can be induced, the optimal number of doses and interval between vaccinations is also not known. The EUA was granted for the 2-dose 100 mcg regimen evaluated in the Phase 3 placebo-controlled clinical trial of mRNA-1273 (NCT04470427, the COVE study), and 100 mcg is the dosage likely to be used in the future if additional mRNA-1273 vaccinations are recommended. Therefore, the 100 mcg dosage was selected for evaluation in this substudy.

## **12.3 Risk/Benefit Assessment**

### **12.3.1 Known Potential Risks**

The potential risks of participating in this substudy are those associated with having blood drawn, IM injection, possible reactions to mRNA-1273, and breach of confidentiality. These and additional risks are described in [Section 2.2.1](#).

A third vaccination of mRNA-1273 has not been evaluated in humans. The risks are expected to be similar to the risks associated with the first and second mRNA-1273 vaccinations in the main study but it is possible that there may be unanticipated risks with the third mRNA-1273 vaccination.

In a prior Phase 1 dose-ranging study of CMV vaccines (mRNA-1647 and mRNA-1443) with doses administered at 0, 1, and 6 months (NCT03382405), no safety issues were identified after the late third dose of mRNA vaccine (at 6 months after initial dose).

### 12.3.2 Known Potential Benefits

As outlined in [Section 12.2](#), data from the Phase 3 placebo-controlled clinical trial of mRNA-1273 (COVE) suggests 94.1% efficacy of the vaccine when administered at 100 mcg versus placebo against SARS-CoV-2 infection when assessed on November 25, 2020 (Baden LR et al, 2020). The efficacy of other doses of mRNA-1273 (e.g., 25, 50, or 250 mcg) is not known. Although declines in binding and neutralizing antibodies are observed over time, 100 mcg of mRNA-1273 has the potential to provide durable humoral immunity (Widge AT et al, 2020).

Administration of a third dose of 100 mcg of mRNA-1273 vaccine might boost cellular responses and binding and neutralizing antibody titers in prior mRNA-1273 recipients. This could provide a boost in immune responses in subjects that received a lower vaccine dose (i.e., 25 mcg, 50 mcg) than that used in the Phase 3 placebo-controlled clinical trial of mRNA-1273 (COVE). Additionally, this third mRNA-1273 vaccination of prior 100 mcg or 250 mcg 2-dose recipients could boost the immune responses directed against the Spike protein of SARS-CoV-2. It is unknown as to whether a third mRNA-1273 vaccination will provide additional protection against SARS-CoV-2 infection.

There is potential benefit to society as a result of information gained from participation in this optional third mRNA-1273 vaccination substudy. Data on the safety and immunogenicity of a third mRNA-1273 vaccination of mRNA-1273 could provide key insights to inform the response to the ongoing threat imposed by the SARS-CoV-2 pandemic.

## 12.4 Objectives and Endpoints

**Table 12: Objectives and Endpoints (Outcome Measures)**

OBJECTIVES	ENDPOINTS (OUTCOME MEASURES)
Primary	

 
To evaluate the safety and reactogenicity of a third mRNA-1273 vaccination, at a dosage of 100 mcg.
 
	
 
Frequency and grade of each solicited local and systemic reactogenicity AE during a 7-day follow-up period post third mRNA-1273 vaccination.
 
Frequency and grade of any unsolicited AEs during the 28-day follow-up period post third mRNA-1273 vaccination.
 
Frequency of any SAEs, Protocol Specified AESIs, NOCMCs, and MAAEs from Substudy Day 1 to Substudy Day 366.
 

Secondary	

OBJECTIVES	ENDPOINTS (OUTCOME MEASURES)

 
To evaluate the immunogenicity as measured by IgG ELISA to the SARS-CoV-2 S (spike) protein following a third mRNA-1273 vaccination, at a dosage of 100 mcg, at all timepoints after the third mRNA-1273 vaccination.
 
	
 
GMT of antibody at each timepoint after the third mRNA-1273 vaccination.
 
Percentage of subjects who seroconverted, defined as a 4-fold change in antibody titer from the pre-third mRNA-1273 dose baseline (Substudy Day 1) at each post-vaccination timepoint and pre-first mRNA-1273 dose baseline (Main Study Day 1).
 
The GMFR in IgG titer from the pre-third mRNA-1273 dose baseline (Substudy Day 1) at each post-vaccination timepoint and pre-first mRNA-1273 dose baseline (Main Study Day 1).
 

Exploratory	

 
To evaluate the immunogenicity as measured by pseudovirus neutralization and other viral neutralization assays following a third mRNA-1273 vaccination, at a dosage of 100 mcg.
 
	
 
GMT of Neut antibody at each timepoint after the third mRNA-1273 vaccination.
 
Percentage of subjects who seroconverted, defined as a 4-fold change in Neut antibody titer from the pre-third mRNA-1273 dose baseline (Substudy Day 1) at each post-vaccination timepoint and pre-first mRNA-1273 dose baseline (Main Study Day 1).
 
The GMFR Neut antibody titer from the pre-third mRNA-1273 dose baseline (Substudy Day 1) at each post-vaccination timepoint and pre-first mRNA-1273 dose baseline (Main Study Day 1).
 

OBJECTIVES	ENDPOINTS (OUTCOME MEASURES)

 
To evaluate the immunogenicity as measured by live SARS-CoV-2 neutralization following a third mRNA-1273 vaccination, at a dosage of 100 mcg.
 
	
 
GMT of Neut antibody at each timepoint after third mRNA-1273 vaccination.
 
Percentage of subjects who seroconverted, defined as a 4-fold change in Neut antibody titer from the pre-third mRNA-1273 dose baseline (Substudy Day 1) at each post-vaccination timepoint and pre-first mRNA-1273 dose baseline (Main Study Day 1).
 
The GMFR in Neut antibody titer from the pre-third mRNA-1273 dose baseline (Substudy Day 1) at each post-vaccination timepoint and pre-first mRNA-1273 dose baseline (Main Study Day 1).
 

 
To assess, in at least a subset of samples, the SARS-CoV-2 S protein-specific T cell responses.
 
	
 
Magnitude, phenotype, and percentage of cytokine producing S protein-specific T cells, as measured by flow cytometry at timepoints pre- and post-third mRNA-1273 vaccination.
 

 
To evaluate using a multiplex assay IgG ELISA to SARS-CoV-2 S protein and SARS-CoV-2 N protein.
 
	
For each antigen,
 
 
GMT of antibody at each timepoint after the third mRNA-1273 vaccination.
 
Percentage of subjects who seroconverted, defined as a 4-fold change in antibody titer from the pre-third mRNA-1273 dose baseline (Substudy Day 1) at each post-vaccination timepoint and pre-first mRNA-1273 dose baseline (Main Study Day 1).
 
The GMFR in IgG titer from the pre-third mRNA-1273 dose baseline (Substudy Day 1) at each post-vaccination timepoint and pre-first mRNA-1273 dose baseline (Main Study Day 1).
 

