ModernaTX, Inc. has developed a rapid response, proprietary messenger RNA (mRNA)-based vaccine platform. This is based on the principle and observations that antigens can be produced *in vivo* by delivery and uptake of the corresponding mRNA by cells. The mRNA then undergoes intracellular ribosomal translation to endogenously express the protein antigen(s) encoded by the vaccine mRNA. This mRNA-based vaccine does not enter the cellular nucleus or interact with the genome, is nonreplicating, and expression is transient. mRNA vaccines thereby offer a mechanism to stimulate endogenous production of structurally intact protein antigens in a way that mimics wild-type viral infection and are able to induce good immune responses against infectious pathogens such as cytomegalovirus (CMV) (NCT03382405), human metapneumovirus (hMPV) and parainfluenza virus type 3 (PIV3) (NCT03392389) and influenza virus (NCT03076385 and NCT03345043). ModernaTX, Inc. is using its mRNA-based technology to develop a novel LNP-encapsulated messenger RNA (mRNA)-based vaccine against SARS-CoV-2. mRNA-1273 is a novel LNP mRNA-based vaccine that encodes for the full-length spike (S) protein of SARS-CoV-2, modified to introduce two proline residues to stabilize the S protein into a pre-fusogenic form.

The coronavirus spike (S) protein mediates attachment and entry of the virus into host cells, making it a primary target for neutralizing antibodies that prevent infection (Johnson et al. 2016; Wang et al. 2016; Wang et al. 2015; Wang et al. 2018; Chen et al. 2017; Corti et al. 2015; Yu et al. 2015; Kim et al. 2019; Widjaja et al. 2019). The Vaccine Research Center (VRC) and collaborators have identified 2 proline mutations at the apex of the S2 central helix that stabilize the S protein in its prefusion conformation (S-2P) (Pallesen et al. 2017). These mutations have been applied to 9 diverse coronaviruses from three coronavirus genera and found to stabilize the prefusion conformation and improve protein expression. Since this mutation has consistently stabilized other beta-CoV S proteins, this mutation was applied to the SARS-CoV-2 S protein. The VRC and collaborators found that the stabilized SARS-CoV-2 S-2P expressed well and is in the prefusion conformation based on negative-stain electron microscopy.

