## 12.9 Immunogenicity Evaluations

### Serological Immunogenicity Assays:

The following serological immunogenicity assays may be performed on specimens collected on the day of and following the third mRNA-1273 vaccination:

- IgG ELISA to the SARS-CoV-2 S (spike) protein(s) and SARS-CoV-2 N protein.
- Pseudovirus and live SARS-CoV-2 neutralization assays.

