### **12.11.3 Populations for Analyses**

The Safety Analysis population includes all subjects who received the third mRNA-1273 vaccination.

The modified intent-to-treat (mITT) population includes all subjects who received of the third mRNA-1273 vaccination and contributed both pre- and at least one post-third mRNA-1273 vaccination venous blood samples for immunogenicity testing for which valid results were reported.

In the final analysis, protocol deviations will be reviewed to determine which protocol deviations may affect the analysis. The per protocol (PP) population will then be defined – and this includes all subjects in the mITT subset with the following exclusions:

- Data from all available visits for subjects found to be ineligible at the time of the third mRNA-1273 vaccination.
- Data from all substudy visits subsequent for the protocol deviations that are considered to affect the science.
- Data from any substudy visit that occurs substantially out of window.

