### **12.11.13 Exploratory Analyses**

Summaries and analysis of immunogenicity data will be presented for the mITT population. If there are protocol deviations which may affect the analysis, a PP analysis may also be performed.

GMFR and seroconversion analyses will be done using two definitions of baseline. Baseline 1 will be considered Main Study Day 1 prior to the first mRNA-1273 vaccination (pre-first mRNA-1273 dose baseline) and baseline 2 will be considered Substudy Day 1 prior to the third mRNA-1273 vaccination (pre-third mRNA-1273 dose baseline).

Seroconversion is defined as a 4-fold increase in antibody titer over baseline.

Seroconversion rates, GMFR and GMT for SARS-CoV-2 as measured by IgG ELISA, neutralization assay using SARS-CoV-2 pseudovirus, neutralization assay using live SARS-CoV-2, and multiplex assay IgG ELISA to the SARS-CoV-2 S proteins and SARS-CoV-2 N protein will be calculated for all post third mRNA-1273 timepoints by cohort and will be summarized graphically. Seroconversion rates, GMFR and GMT will be presented with their corresponding 95% CI estimates at each post-vaccination timepoint and overall peak GMT.

Summaries and analysis of cellular assay data will be presented for the mITT population. If there are protocol deviations which may affect the analysis, a PP analysis may also be performed.

The magnitude, phenotype and percentage of cytokine producing S protein-specific T cells will be summarized at each post-vaccination timepoint by vaccination group.

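### The substudy measures N-protein IgG but has no rule for using it to identify spike and neutralization titers taken after a post-third-dose infection, so late results may overstate persistence by an unknown amount

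*Protocol*

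**What the plan says.** Protocol 2.1 describes the product: "mRNA-1273 is a novel LNP mRNA-based vaccine that encodes for the full-length spike (S) protein of SARS-CoV-2". It has no N component.

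Table 12 in Protocol 12.4 sets spike IgG as the secondary immunogenicity objective, with endpoints that include "GMT of antibody at each timepoint after the third mRNA-1273 vaccination". Its last exploratory objective is "To evaluate using a multiplex assay IgG ELISA to SARS-CoV-2 S protein and SARS-CoV-2 N protein". For each of the two antigens it lists GMT, the percentage with a 4-fold change, and the geometric mean fold rise (GMFR). Section 12.11.13 applies this to the "multiplex assay IgG ELISA to the SARS-CoV-2 S proteins and SARS-CoV-2 N protein will be calculated for all post third mRNA-1273 timepoints by cohort". Section 12.11.7 takes the spike summaries through Substudy Day 366.

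Protocol 12.9 leaves the assays optional: "The following serological immunogenicity assays may be performed on specimens collected on the day of and following the third mRNA-1273 vaccination".

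On infection, 12.6.2 excludes documented COVID-19 at substudy entry, and nothing in 12.11 deals with infection after the third dose. The modified intent-to-treat (mITT) definition in 12.11.3 has no infection rule. The per-protocol (PP) definition removes subjects ineligible at the third dose, visits substantially out of window, and "Data from all substudy visits subsequent for the protocol deviations that are considered to affect the science".

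The supplied SAP covers the main study only. Protocol 12.11.4 promises a full substudy SAP before the final data lock.

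**The concern.** The N result is the one planned measurement that could show which subjects were infected after the third dose, and the plan uses it only to describe cohorts. Catching COVID-19 is not a protocol deviation, does not make a subject ineligible at the time of the third dose, and does not put a visit out of window. Followed as written, the plan keeps every post-infection titer in both mITT and PP.

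Other routes to detection are weak. After Substudy Day 29 only serious, protocol-specified special-interest, medically attended and new-onset chronic events are reported (Protocol 12.10.1), and Table 14 schedules no virological testing. A mild case without a medical visit, or a silent infection, need not appear anywhere except in N serology.

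The persistence question matters here. Section 12.1 gives as one reason for the substudy "To potentially enhance and extend the duration of protection provided by the 2-dose vaccination schedule", and 12.2 calls durability of the response uncertain. Section 12.5 foresees comparing the 25 and 50 mcg cohorts with the 100 mcg cohort, and 12.7.2 says that a response judged suboptimal could lead to an amendment. The third dose is offered to the lower-dose cohorts soon after Main Study Day 209, and to the 100 and 250 mcg cohorts up to the close of the Day 394 window. Calendar exposure to infection can therefore differ along the axis being compared.

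**Working it through.** **The plan's own figures.** The documents give no infection count, expected infection rate or titer effect for the substudy. Its only stated probabilities (Protocol 12.11.2) concern adverse events, and they reproduce: 1 − 0.97^120 = 97.4% (stated as about 97%) and 1 − 0.8^5 = 67.2% (stated as about 67%). They do not bear on this point.

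**Inputs.**
- Subjects: 120 enrolled (12.2), less 4 without a second dose (footnote to Table 13), leaves at most 116. By cohort the maximum is 9 to 15.
- Symptomatic COVID-19 in the Phase 3 trial (12.2): 3.3 per 1000 person-years in the vaccine arm (95% CI 1.7 to 6.0) and 56.5 in the placebo arm.
- Fold rise k in a subject's titer after infection: not in the documents. Assumed 2 to 20.
- Exposure: assumed one year for all 116.

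**Expected cases.** Expected number = 116 × rate; P(at least one) = 1 − exp(−expected number).

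| Rate per 1000 person-years | Expected cases | P(at least one in 116) | P(at least one in a cohort of 10) |
|---|---|---|---|
| 1.7 (vaccine arm, lower limit) | 0.20 | 18% | 1.7% |
| 3.3 (vaccine arm) | 0.38 | 32% | 3.2% |
| 6.0 (vaccine arm, upper limit) | 0.70 | 50% | 5.8% |
| 56.5 (placebo arm, upper illustration only) | 6.55 | 99.9% | 43% |

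These count symptomatic cases only. Asymptomatic infections would add to them by an amount the documents do not give.

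**Effect on a cohort GMT.** If m of n subjects have their titer multiplied by k, the mean log titer rises by (m/n) × log k, so observed GMT divided by infection-free GMT = k^(m/n). For k above 1 the bias is always upward. GMFR is inflated by the same factor, because either baseline precedes the infection.

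| Cohort, cases | k = 2 | k = 4 | k = 10 | k = 20 |
|---|---|---|---|---|
| 10, one case | 1.07 | 1.15 | 1.26 | 1.35 |
| 10, two cases | 1.15 | 1.32 | 1.58 | 1.82 |
| 15, one case | 1.05 | 1.10 | 1.17 | 1.22 |
| 15, two cases | 1.10 | 1.20 | 1.36 | 1.49 |

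**Effect on apparent waning.** In a cohort of 10 with k = 10, a true 4-fold decline would appear as 4/1.26 = 3.2-fold with one case and 4/1.58 = 2.5-fold with two.

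**The case against.** The strongest reply is that the bias is conditional and probably small. At the only rate in vaccinees that the documents give, the chance of any symptomatic case in a given cohort of 10 over a year is about 3%. The chance of two or more is about 0.033²/2 = 0.05%. At Day 91 only about 116 × 0.0033 × 90/365 = 0.09 cases would be expected in the whole substudy. This stands, subject to the unknown number of asymptomatic infections.

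A reader might infer from the placebo-arm rate that 6.6 cases, or a 43% chance per cohort of 10, should be expected. The documents do not support that: the rate comes from unvaccinated subjects and can serve only as an upper illustration.

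Two further replies have partial force. The planned percentage with a 4-fold N rise by cohort and visit already comes close to a count of infections. It still does not connect a subject's infection to that subject's spike titers. Also, the substudy SAP is still to be written and all data will be listed by subject (12.11.12), so one cannot conclude that N will never be used this way. However, that SAP is due only before final lock, while 12.5 and 12.11.10 allow interim review and publication earlier. The rule is better fixed before late titers are seen.

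Finally, leaving out results after infection conditions on a post-baseline event. If low responders are infected more often, the reduced set is itself biased upward. This stands, and is why the reduced analysis should supplement the all-data one.

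**Conclusion.** The gap is real in the protocol text. N IgG is planned only as a further by-cohort antibody endpoint, and no rule in 12.11 uses it to identify spike or neutralization titers measured after a post-third-dose infection. Late GMT, GMFR and 4-fold-rise results may overstate persistence of the third-dose response.

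A reader might go further and infer that the Day 91 to 366 results do overstate durability. The documents do not support that. It requires infections that raise spike titers, and neither their number nor their effect is given. At the vaccine-arm rate there is about a two-in-three chance of no symptomatic case at all.

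The size rests on three assumptions: full participation by 116 subjects for a year, Phase 3 symptomatic rates carried over to the substudy, and a 2- to 20-fold titer rise. Fewer participants would lower the expected count but raise the effect of each case on its cohort. The substudy tests no hypothesis and its primary objective is safety, so this is a worthwhile improvement to an immunogenicity summary and not a flaw in the main result.

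**What to change.** In Protocol 12.11.7 and 12.11.13, and in the substudy SAP, define post-third-dose infection as documented COVID-19 or N seroconversion. Seroconversion here means a 4-fold or greater rise over Substudy Day 1, or crossing the assay's positivity cut-off. Keep the all-data summaries. Beside them, add a supplementary version of the spike IgG and neutralization summaries that leaves out a subject's results from the first such visit onward, and report the number infected per cohort and visit. Protocol 9.3 already uses this with-and-without logic for safety data after a third dose or a non-study vaccine.

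In 12.9, change the N assay from one that may be run to one that will be run, at Substudy Day 1 and at the later visits.

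No new blood draws are needed, since Table 14 takes serum for humoral assays at every substudy visit. The costs are the commitment to an assay that is now optional, slightly smaller numbers at late visits in the supplementary version, and the possible selection effect described above. Showing both versions lets the reader judge that effect.
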